8.6.2. Clinical Laboratory Parameters

All clinical laboratory evaluations, with changes from baseline, will be listed; any value outside the clinical reference range will be flagged, and whether the out of range value was deemed clinically significant or not clinically significant will be indicated. Separate listings will be provided for any parameter for which there is any individual subject value outside the respective clinical reference range.

The observed results and change from baseline for clinical chemistry, hematology, and coagulation parameters will be summarized descriptively by treatment and timepoint.

Values recorded as $< x$, $\leq x$, $> x$, or $\geq x$ will be displayed in the listings as recorded. For the derivation of listing flags, calculation of summary statistics, and presentation in the figures, $< x$ and $\leq x$ values will be set to 0, whereas $> x$ and $\geq x$ values will be set to x .

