3. Abnormal laboratory values (hematology panel, UA, clinical chemistry panel [fasted at least 8 hours], excluding those further defined in exclusion criteria #5, #6, #7, and #8 below) determined to be clinically significant by the Investigator (or designee), and Sponsor at Screening and/or Check-in (Day -1) as confirmed by repeat assessment.
4. Clinically significant abnormality, as determined by the Investigator (or designee), from physical examination at Check-in (Day -1).
5. Abnormal liver function tests (LFTs), as defined by aspartate aminotransferase, alanine aminotransferase, and serum (total and direct) bilirubin, as well as amylase and lipase above the upper limit of the normal range at Screening or Check-in (Day -1). Rechecks of LFTs, amylase, and lipase will be permitted up to 2 times to confirm eligibility for study participation if the values fall within normal ranges.
6. Any clinically significant deviations from normal ranges in creatine kinase (CK) unless approved by the Investigator (or designee) and Sponsor. Rechecks of CK will be permitted up to 2 times to confirm eligibility for study participation if the out-of-range values are stable or trending down and the Investigator (or designee) and the Sponsor deem that the results are not clinically significant and will not impact study conduct.

7. Estimated glomerular filtration rate \leq 90 mL/minute/1.73m² at Screening or Check-in (Day -1) calculated using the Chronic Kidney Disease Epidemiology Collaboration equation.
8. Hemoglobin, white blood cell count, and platelet counts below the lower limit of normal range at Screening or Check-in (Day -1). Rechecks of hemoglobin, white blood cell count, and platelet counts will be permitted up to 2 times to confirm eligibility for study participation if the values fall within normal ranges.
9. Positive serologic test for HBsAg, HBV core antibody, HCV, or HIV antibody at Screening. Subjects who are positive for HCV by antibody will require confirmation by PCR before enrollment to detect presence of active virus. Subjects who are HCV PCR positive or for whom a PCR is unable to be obtained will not be eligible.
10. Positive PCR test (or equivalent) for COVID-19 at Screening or Check-in (Day -1). Further details regarding COVID-19 testing (including procedures who test positive at any time throughout CRU confinement) are specified in separate documents.

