Appendix 2: Clinical Laboratory Evaluations

Clinical Chemistry Panel (Fasted):	Hematology Panel:	Other Tests:
Alanine aminotransferase (ALT) Albumin Alkaline phosphatase (ALP) Amylase Aspartate aminotransferase (AST) Bilirubin (direct and total) Blood urea nitrogen Calcium Chloride Cholesterol Creatine kinase Creatinine Glucose Iron Lipase Magnesium Phosphorus Potassium Sodium Total protein Triglycerides Uric acid	Hematocrit Hemoglobin Mean corpuscular hemoglobin Mean corpuscular hemoglobin concentration Mean corpuscular volume Platelet count Red blood cell (RBC) count RBC distribution width White blood cell (WBC) count WBC differential (percent and absolute): Basophils Eosinophils Lymphocytes Monocytes Neutrophils	Hemoglobin A1c (HbA1c) ^b Thyroid-stimulating hormone (TSH) ^b Estimated glomerular filtration rate ^a SARS-CoV-2 (COVID-19) Testing
		Coagulation Parameters: Partial thromboplastin time Prothrombin time International normalized ratio
		Serology: Human immunodeficiency virus (HIV) antibody Hepatitis B surface antigen (HBsAg) Hepatitis B virus (HBV) core antibody Hepatitis C virus (HCV) antibody
		For Female Subjects only: Pregnancy test (serum qualitative, serum quantitative may be used for confirmation if needed) ^c Follicle-stimulating hormone (post-menopausal female subjects only) ^b
Urine Drug Screen: ^a	Bilirubin Color and appearance Glucose Ketones Leukocyte esterase Nitrite Occult blood pH and specific gravity Protein Urobilinogen Microscopic examination including bacteria, casts, crystals, epithelial cells, RBCs, and WBCs (if protein, leukocyte esterase, nitrite, or blood is positive)	

a. Performed at Screening and Check-in (Day -1) only.

- a. Performed at Screening and
- b. Performed at Screening only.

c. Performed at Screening, Check-in (Day -1), and End of Treatment (EOT) or Early Termination (ET) only.

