5. SAMPLE SIZE JUSTIFICATION

This study is planned to enroll up to 24 healthy adult male and female subjects (women of non-childbearing potential only). Six subjects will participate in each cohort.

Replacement subjects may be enrolled only if deemed necessary by the Sponsor.

Every attempt will be made to enroll at least 1 subject of each sex in each cohort.

No formal statistical assessment of sample size has been conducted. The sample size chosen for this study is common in single-ascending dose studies and is considered sufficient to achieve the objectives of the study.

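### SAP 8.6.2 sets laboratory results reported only as a limit to 0 or to that limit before deriving flags and summaries, which can produce false or missed flags and puts the lowest possible value into means and changes

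*SAP*

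**What the plan says.** SAP 8.6.2 covers laboratory results that arrive as `<x`, `≤x`, `>x` or `≥x`. In the listings they "will be displayed in the listings as recorded". For three other uses they are first replaced by a number: "For the derivation of listing flags, calculation of summary statistics, and presentation in the figures". For `<x` and `≤x` the text is "values will be set to 0, whereas" `>x` and `≥x` take the value x. No analyte is exempt, and no reason is given for the choice.

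The same section states what the substituted values feed into:

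- **Flags.** "any value outside the clinical reference range will be flagged, and whether the out of range value was deemed clinically significant" or not is to be indicated. Any parameter with at least one out-of-range value also gets a separate listing.
- **Tables.** "The observed results and change from baseline for clinical chemistry, hematology, and coagulation parameters will be summarized descriptively by treatment and timepoint". Urinalysis is not among the summarized panels.

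On cohort size, SAP section 5 says "Six subjects will participate in each cohort". SAP 8.6.6 plans no inferential safety analysis. Protocol Appendix 2 names the analytes but gives no reporting limits or reference ranges.

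**The concern.** A result of `<x` is an interval, not a number. Replacing it by 0 before testing it against the reference range means that the flag comes from a value the laboratory did not report. If the interval straddles a reference limit, the report does not say whether the subject is out of range, yet the rule gives a definite answer. At the upper end, `>x` loses its strict inequality and becomes x, so a result known to be high can go unflagged.

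In the tables, 0 is the bottom of the possible range for `<x`, and x is the bottom of the range for `>x`. Both substitutions therefore pull in the same direction. The two ends are also treated inconsistently: `≥x` is set to x, while `≤x`, which may be exactly x, is set to 0. For coagulation times, 0 is not a possible value.

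Safety is the primary objective, and laboratory evaluations are one of the assessments named under the primary endpoint. With six subjects per cohort and only descriptive tables, a single substituted value can carry visible weight. The SAP asks for no count that would show the reader of a table where substitution occurred.

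**Working it through.** The documents state no figure for this point, so there is none to reproduce.

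**Inputs.** The substitution and flag rules are from SAP 8.6.2, and n = 6 per cohort is from SAP 5. The reporting limit x, the reference limits LLN and ULN, and the number k of limit-only results are not in the documents. They are symbols or assumed values here. Values are assumed not to fall below 0.

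**Flags.** A value is low if it is below LLN and high if it is above ULN. Taking each possible position of x:

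| Reported | Position of x | Flag under the rule | What the report supports |
|---|---|---|---|
| `<x` | LLN = 0 | no low flag | right: cannot be low |
| `<x` | x ≤ LLN, LLN > 0 | low | right: certainly low |
| `<x` | 0 < LLN < x | low | unsettled: false if the true value is between LLN and x |
| `>x` | x > ULN | high | right: certainly high |
| `>x` | x = ULN | none | certainly high: missed |
| `>x` | LLN ≤ x < ULN | none | unsettled: may be high |
| `>x` | x < LLN | low | unsettled: may be false |

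`≤x` behaves like `<x`, except that at x = LLN the low flag may also be false, because the result can equal LLN. `≥x` behaves like `>x`, except that at x = ULN a high is possible and not certain. The upper-end rule never creates a false high flag.

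For scale, with assumed LLN = 2 and x = 3 and true values uniform from 0 to 3, the share of false low flags is (3 − 2)/3 = 1/3.

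**Means.** If k of 6 results are `<x` and are set to 0, the mean shifts by −(sum of the k true values)/6, which lies between 0 and −(k/6)x.

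- k = 1: up to x/6 = 0.167x (0.083x if the true value is x/2)
- k = 3: up to 0.5x
- k = 6: up to x

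Assumed example: five results of 0.3 and one `<0.2`.

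- Under the rule: mean (5 × 0.3 + 0)/6 = 0.250, SD 0.122.
- With the limit in place of 0: mean (5 × 0.3 + 0.2)/6 = 0.283, SD 0.041.

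The true mean lies between 0.250 and 0.283. The substitution alone changes the SD threefold.

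**Change from baseline.** A baseline of `<x` followed by x gives x − 0 = +x, while the true change lies anywhere from just above 0 up to x. At the upper end, a baseline y followed by `>x` gives x − y, which is the lower bound of the true rise. The shortfall has no upper limit.

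**The case against.** The strongest reply is that nothing shows the rule will do harm here. Without reporting limits and reference ranges, no false or missed flag can be shown for any analyte, and some positions of x give the right flag. The listings keep the reported result beside the clinical-significance assessment, so with six subjects an artefact can be traced by hand. Laboratory abnormalities become adverse events on the investigator's judgement, and dose escalation rests on review of the safety data by the investigator and sponsor. Neither is tied to a derived flag. Which single number to use for a limit-only result is largely convention, and SAP 8.5.2 also uses 0 for unquantifiable plasma concentrations in its summaries.

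Most of this stands and sets the size of the point. It does not remove it. The listing lets a reader repair a flag but does nothing for the table, which carries no sign that a value was substituted. The plasma-concentration rule is a weak precedent: a drug concentration can truly be 0, and there the SAP withholds the geometric mean whenever such a value is present.

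Three stronger readings are tempting and are not supported:

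- **Eligibility.** A reader might infer that "Estimated glomerular filtration rate" reported as `>90` would become 90 and so meet exclusion criterion 7. Eligibility is decided at Screening and Check-in. SAP 8.6.2 governs reporting outputs, and its flags refer to reference ranges and not to entry criteria.
- **Urinalysis means.** "pH and specific gravity" cannot be 0, so a reader might expect absurd averages. Urinalysis has no summary table under SAP 8.6.2, so only a listing flag or a listed change could be affected.
- **Half the limit as the remedy.** Setting `<x` to x/2 is another convention. It still gives impossible values for such analytes, and it does not cure flags: with LLN = 2 and x = 3, x/2 = 1.5 is still flagged low.

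**Conclusion.** The point holds in conditional form. Where limit-only results occur, the rule can give a false low flag (`<x` with 0 < LLN < x, or `>x` with x < LLN). It misses a certain high for `>x` with x = ULN and may miss one with x < ULN. It also puts the lowest possible value into means and changes from baseline: up to x/6 on a six-subject mean for each `<x`, and +x for a move from `<x` to x.

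A reader might go further and say that the rule will produce spurious flags in this trial. The documents do not support that, because they give neither reporting limits nor reference ranges, and the frequency may be low. The effect is confined to derived flags, descriptive tables and figures. It is still worth correcting, since these are the planned laboratory outputs for the primary objective and the correction is cheap.

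**What to change.** In SAP 8.6.2, separate flags from summaries.

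- **Flags.** Compare the whole reported interval with the reference range. Flag low or high only if the interval lies entirely outside on that side. Leave it unflagged if it lies entirely inside, and mark it indeterminate otherwise. This removes the false low flags and recovers the certain high at `>x` with x = ULN.
- **Summaries and figures** for chemistry, hematology and coagulation. Use x for `<x` and `≤x`, matching the existing treatment of `>x` and `≥x`.
- **Counts.** Show the number of limit-only results in each table cell, for observed values and for changes.

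The downside of using x is an upward bias in means with low-end limits: at most x/6 per value in a six-subject cohort, the same bound as with 0 but in the other direction. A move from `<x` to x would be shown as 0, which may understate a real rise. Neither number is right in general, so the count matters more than the choice, although x avoids impossible zeros and treats both ends alike.

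The cost is a few sentences in the SAP, a count in the table shells and a small programming change before database lock.

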8.6.3. Vital Signs Results

All vital sign results with changes from baseline will be listed; any value outside the clinical reference range will be flagged, and whether the out of range value was deemed clinically significant or not clinically significant will be indicated.

The observed results and change from baseline for all vital signs results will be summarized descriptively by treatment and timepoint.

8.6.4. 12-lead Electrocardiogram Parameters

All 12-lead ECG parameters with changes from baseline will be listed; any value outside the clinical reference range will be flagged, and whether the out of range value was deemed clinically significant or not clinically significant will be indicated.

The observed results and change from baseline for all 12-lead ECG parameters will be summarized descriptively by treatment and timepoint. QTcF values that are > 450 msec and increase from baseline > 30 msec will be flagged in the data listing.

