4.4. Exclusion Criteria

The following will exclude potential subjects from the study:

1. History or presence of any of the following, deemed clinically significant by the Investigator (or designee) and/or Sponsor:
 - a. liver disease
 - b. pancreatitis
 - c. peptic ulcer disease
 - d. intestinal malabsorption
 - e. cholecystectomy
 - f. gastric reduction surgery
 - g. history or presence of clinically significant cardiovascular disease:
 - i. Myocardial infarction or cerebrovascular thromboembolism within 6 months prior to the first dose administration (Day 1)
 - ii. Symptomatic angina pectoris within 6 months prior to the first dose administration (Day 1)
 - iii. New York Heart Association Class ≥ 2 congestive heart failure within 6 months prior to the first dose administration (Day 1)
 - iv. Congenital prolonged QT syndrome
 - v. Ventricular pre-excitation syndrome (Wolff-Parkinson White syndrome)
 - vi. Arrhythmia (excluding benign sinus arrhythmia) or history of arrhythmia requiring medical intervention
 - vii. Ventricular dysfunction or risk factors for Torsades de Pointes (eg, heart failure, cardiomyopathy, family history of Long QT Syndrome)

viii. Significant screening ECG abnormalities:

1. left bundle branch block
2. second degree atrioventricular (AV) block, type 2, or third-degree AV block
3. QT interval corrected for heart rate using Fridericia's method (QTcF) is > 450 msec
4. ECG findings deemed abnormal with clinical significance by the Investigator (or designee) at Screening, Check-in (Day -1), or prior to dosing on Day 1.

2. Subjects with out-of-range, at-rest (ie, supine for at least 5 minutes) vital sign measurements at Screening, Check-in (Day -1), or prior to dosing on Day 1, including:
 - a. oral body temperature > 37.5°C;
 - b. pulse rate < 50 or > 99 beats per minute (bpm);
 - c. systolic BP < 89 or > 139 mmHg;
 - d. diastolic BP < 50 or > 89 mmHg;
 - e. oxygen saturation < 95% (room air)

For these parameters, out-of-range values that are not clinically significant (as determined by the Investigator [or designee]) may be repeated twice during Screening, Check-in (Day -1), and predose on Day 1. Note: Rechecks of pulse rate and BP values will be permitted up to 2 times to confirm eligibility for study participation. Subjects may be eligible for participation in the study based on rechecked pulse rate and/or BP values if the values fall within the ranges stated above.

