Appendix 4: Schedule of Assessments

Study Procedures ^a	Screening (Days -29 to -2)	Check-in (Day -1)	Study Conduct							Clinic Discharge/ EOT/ET ^t	Follow-up Phone Call (EOS)
			1	2	3	4	5	6	7		
Confined to the CRU		X	X	X	X	X	X	X	X	X	
Inclusion/Exclusion Criteria	X	X									
Informed Consent	X										
Demographics	X										
Medical History	X	X ^b									
Height/Weight/BMI	X ^c	X ^c									
Physical Examination ^d		X								X	
12-lead ECG ^e	X	X	X	X		X				X	
Vital Signs ^f	X ^{g,h}	X ^{g,h}	X ^h	X	X	X	X	X	X	X ^{g,h}	
HDYF? Inquiry ⁱ	X	X	X	X	X	X	X	X	X	X	X
AEs/SAEs ^j	X	X	X	X	X	X	X	X	X	X	X
LOXO-305 Administration			X ^k								
CCI											
Clinical Laboratory Evaluations ⁿ	X	X				X				X ^u	X ^u
Estimated Glomerular Filtration Rate	X	X									
Hepatitis and HIV Screen	X										
COVID-19 Testing ^o	X	X									
HbA1c Test	X										
Drug Screen ^p	X	X									
Prior and Concomitant Medications ^q	X	X	X	X	X	X	X	X	X	X	X
Serum Pregnancy Test ^r	X	X								X ^u	X ^u
FSH Test ^s	X										
TSH Test	X										

Abbreviations: AE = adverse event; BMI = body mass index; BP = blood pressure; COVID-19 = SARs Coronavirus 19; CRU = Clinical Research Unit; ECG = electrocardiogram; EOS = End of Study; EOT = End of Treatment; ET = Early Termination; FSH = follicle-stimulating hormone; HbA1c = hemoglobin A1c; HDYF? = How Do You Feel?; HIV = human immunodeficiency virus; ICF = Informed Consent Form; PK = pharmacokinetic; SAE = serious adverse event; TSH = thyroid-stimulating hormone; UA = urinalysis.

- a. For details on study procedures, see [Section 7](#).
- b. Interim medical history only.
- c. Height collected at Screening only, body mass index based on Screening height.
- d. A complete physical examination will be performed at Check-in (Day -1). An abbreviated physical examination will be performed on Day 8 (End of Treatment [EOT]) or Early Termination (ET).
- e. 12-lead electrocardiograms (ECGs) will be obtained prior to and as close as possible to the scheduled blood draws at Screening and Check-in (Day -1), and at the following times related to administration of each Treatment: Day 1 (predose and 2 and 4 hours after LOXO-305 dosing), Day 2, Day 4, and Day 8 (EOT) or ET. 12-lead ECGs will be collected after the subject has rested in the supine position for at least 10 minutes.

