8. STATISTICAL METHODOLOGY

8.1. General

Listings will be provided for all data captured in the database. Listings will include all subjects assigned to the all subjects population and include data up to the point of study completion or discontinuation. Subjects are generally considered to have completed the study if they completed all protocol-specified procedures and assessments for the EOT visit. Any subject who discontinued the study will be identified accordingly in the listings. Summaries and statistical analyses will include the subjects assigned to the relevant population based on data type.

Data analysis will be performed using the SAS® statistical software package Version 9.4 (or higher if upversioned during the study).

Analysis Data Model (ADaM) datasets will be prepared using Clinical Data Interchange Standards Consortium (CDISC) ADaM Version 2.1 (or higher if upversioned during the study) and CDISC ADaM Implementation Guide Version 1.2 (or higher if upversioned during the study). Pinnacle 21 Community Validator Version 2.2.0 (or higher if upversioned during the study) will be utilized to ensure compliance with CDISC standards.

Caution should be used when interpreting results from the statistical analyses conducted in this study because the sample size is not based on power calculations.

Where reference is made to 'all calculations', this includes, but is not limited to, summary statistics, statistical analyses, baseline derivation, changes from baseline, and any parameter derivations.

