8.1.1. Calculation of the Summary Statistics

For continuous data the following rules will be applied:

- Missing values will not be imputed, unless specifically stated otherwise.
- Unrounded data will be used in the calculation of summary statistics.
- If the number of subjects with valid observations ($n < 3$), summary statistics will not be calculated, with the exception of n , minimum, and maximum.
- As ET data is not associated with any scheduled timepoint, it will be excluded from all calculations of summary statistics.
- Postdose repeats and unscheduled assessments will not be included in calculations of summary statistics.

For categorical data the following rules will be applied:

- If the categories of a parameter are ordered (eg, AE severity), all categories between the possible minimum and maximum categories will be included, even if $n = 0$ for a given category. If the categories are not ordered (eg, race), only those categories for which there is at least 1 subject represented will be included.
- Missing values will not be imputed, with the exception of AEs where the 'worst-case' approach will be taken (see [Section 8.6.1](#)), or unless specifically stated otherwise. A 'missing' category will be included for any parameter for which information is missing. This will ensure that the population size totals are consistent across different parameters.

All protocol deviations and data issues (eg missing data, out of protocol window) that occur during the study, including those related to COVID-19, will be considered prior to database lock for their severity/impact on how the data will be displayed.

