8.1.2. Repeat and Unscheduled Assessments

For vital sign measurements and 12-lead ECG data only, any predose value recorded in addition to the original value or a postdose value recorded within 15 minutes of the original value will be defined as a repeat value; any postdose value recorded more than 15 minutes after the original value will be defined as an unscheduled value. For all other data types (eg, clinical laboratory values), any value recorded in addition to the original value will be defined as an unscheduled value.

The original scheduled value will be used in all calculations postdose. In the event of any repeats or unscheduled measurements taken pre-dose the values will be considered when determining the baseline value.

Postdose repeats, unscheduled assessments, and ET measurements will be excluded from all calculations with the exception of the baseline derivation (see [Section 8.1.3](#)).

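### Does the unclear wording of the QTcF listing flag in SAP 8.6.4 put the ECG safety review at risk?

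*SAP*

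**What the plan says.** SAP 8.6.4 gives one QTcF-specific rule: "QTcF values that are > 450 msec and increase from baseline > 30 msec will be flagged in the data listing". The same section gives the wider cover: "All 12-lead ECG parameters with changes from baseline will be listed; any value outside the clinical reference range will be flagged", with an indication of whether each out-of-range value was clinically significant. It also calls for observed values and changes to be summarised by treatment and timepoint.

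Two general rules bear on which readings have a change. SAP 8.1.2 states "Postdose repeats, unscheduled assessments, and ET measurements will be excluded from all calculations", apart from the baseline derivation. SAP 8.1 explains that the phrase about all calculations is broad: "this includes, but is not limited to, summary statistics, statistical analyses, baseline derivation, changes from baseline, and any parameter derivations".

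The ECG times in Protocol Appendix 4 (footnote e), besides Screening and Check-in, are "Day 1 (predose and 2 and 4 hours after LOXO-305 dosing), Day 2, Day 4, and Day 8 (EOT) or ET". Entry is barred at Screening if the "QT interval corrected for heart rate using Fridericia's method (QTcF) is > 450 msec" (Protocol 4.4). SAP 1 places the detailed description of tables, figures and listings in a separate shells document, which is not among the documents available here.

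**The concern.** The word joining the two limits can be read in two ways. It may define one flag that needs both conditions, or it may list two things to be flagged. Nothing in the protocol or SAP settles this, so two programmers could build different listings and both be compliant.

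The joint reading is the weaker screen. A large rise that ends at or below 450 msec would get no mark, and some values above 450 msec would get none if the subject started high.

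A second uncertainty holds under either reading. If change from baseline is not derived for postdose repeat, unscheduled and early-termination ECGs, a change-based mark cannot appear on them. Those readings are also left out of the summaries, so the listing is the only output that shows them.

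The subject matter makes the point look heavier. Safety, including 12-lead ECGs, is the primary endpoint. The study takes healthy subjects to supratherapeutic exposure, partly to help design a possible QT study (Protocol 1.4 and 3.2). The SAP text describes no categorical QTcF table. At stake is whether an individual outlier could be overlooked.

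**Working it through.** **Inputs.** Limits of 450 msec and 30 msec (SAP 8.6.4); baseline B, the last non-missing predose value (SAP 8.1.3); change = value minus B (SAP 8.1.3); screening exclusion above 450 msec (Protocol 4.4), used as an approximate ceiling for B; up to 24 subjects (Protocol 8.1); five scheduled postdose ECG times: 2 h, 4 h, Day 2, Day 4, Day 8 (Protocol Appendix 4). The documents give no figure of their own to reproduce.

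**Joint reading.** A value Q is marked if Q > 450 and Q − B > 30, that is, Q > max(450, B + 30).

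**Separate reading.** Q is marked if Q > 450 or Q − B > 30, that is, Q > min(450, B + 30).

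The two limits cross at B = 450 − 30 = 420. In whole msec:

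| Baseline | Lowest marked, joint | Lowest marked, separate | Marked only under separate |
|---|---|---|---|
| 360 | 451 | 391 | 391–450 |
| 380 | 451 | 411 | 411–450 |
| 400 | 451 | 431 | 431–450 |
| 420 | 451 | 451 | none |
| 430 | 461 | 451 | 451–460 |
| 440 | 471 | 451 | 451–470 |
| 450 | 481 | 451 | 451–480 |

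So at every baseline of 420 or below, the joint rule is the same as the 450 msec limit alone. Above 420 it drops some values over 450.

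**How often this could matter.** This needs a baseline distribution, which the documents do not give. Assume a normal distribution with mean m of 390 to 410 msec and SD s of 15 to 20 msec, truncated at 450. The share of subjects for whom a rise r ends at or below 450 is Φ((450 − r − m)/s) / Φ((450 − m)/s).

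- r = 35: highest at m = 390, s = 15, Φ(1.67)/Φ(4) = 0.952; lowest at m = 410, s = 20, Φ(0.25)/Φ(2) = 0.613.
- r = 45: highest at m = 390, s = 15, Φ(1)/Φ(4) = 0.841; lowest at m = 410, s = 15, Φ(−0.33)/Φ(2.67) = 0.371.
- r = 60: highest at m = 390, s = 20, Φ(0)/Φ(3) = 0.501; lowest at m = 410, s = 15, Φ(−1.33)/Φ(2.67) = 0.092.

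These are shares with no mark from this rule under the joint reading. They are not shares undetected. Under the separate reading all of these rises are marked at scheduled times.

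**What remains visible without the mark.**

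1. Scheduled readings: at most 24 × 5 = 120 postdose values, each listed with its change. A reviewer can read that many directly.
2. Summaries by dose and timepoint include minimum and maximum. SAP 8.1.1 keeps them even with fewer than three observations ("summary statistics will not be calculated, with the exception of n , minimum, and maximum"). The largest scheduled rise in a cohort of six therefore appears as the maximum change at its timepoint, whatever the flag does.
3. Out-of-range values are flagged separately with a significance call, although the QTcF range is not stated.
4. Repeat, unscheduled and early-termination readings are listed, because SAP 8.1 lists all captured data. The 450 msec criterion taken alone needs no derived change. If the change is not printed, it is one subtraction from the listed baseline.
5. Adverse events noted on ECG are recorded as such (Protocol 7.2.1).
6. Escalation requires the Investigator and Sponsor to review the ECGs themselves through 168 hours (Protocol 3.1 and 5.5). Neither section refers to this flag.

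**The case for a change.** The strongest case for acting is that this is the only QTcF-specific outlier rule in the SAP, that the literal reading of the sentence is the joint one, and that the joint reading weakens both limits at once. The general out-of-range flag does not replace it: its limits are not given, and it does not address change. Repeat and unscheduled ECGs are the readings most likely to follow a suspicious trace, and they have the least cover. Clarifying the sentence before database lock would cost almost nothing.

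Much of this stands as description. The wording is unclear, the arithmetic is right, and SAP 8.1.2 and 8.6.4 are not reconciled for the extra readings. Two parts are weaker. First, 8.6.4 promises changes for all ECG parameters without exempting any reading, and SAP 8.6.2 (on laboratory data) treats listing flags and summary statistics as separate uses. The most one can say is that a mark might not appear. Second, the percentages need both the less favourable reading and an assumed baseline distribution, so they do not measure a demonstrated defect.

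What the objection does not show is a result that would come out differently. A count table or higher QTcF tiers would be a preference in a study with six subjects per cohort and no inferential safety analysis.

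**Conclusion.** No change to the plan follows. This is a missing detail in the definition of a listing annotation, and analysts can fill it sensibly: mark values over 450 msec and rises over 30 msec, and show the change wherever a postdose value and a baseline exist. The shells document, where a listing footnote would normally sit, may already say so, but it was not available to check.

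The effect is confined to which of at most about 120 scheduled postdose readings, plus any extra ones, carry a mark. Every value is listed under either reading. Scheduled changes are also listed and summarised, and escalation decisions use the ECGs directly. No estimate, test, summary table or safety conclusion alters.

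The 420 msec crossover is exact and needs no assumption. The ranges of 61–95%, 37–84% and 9–50% for rises of 35, 45 and 60 msec hold only under the joint reading and the assumed baseline distribution. The conclusion does not rest on them.
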